6.3. Doses and Regimens

Treatments for each group are shown in [Table 1](#). Subjects will receive one of the following dose regimens: 5 mg CCX140-B once daily, 10 mg CCX140-B twice daily, 15 mg CCX140-B twice daily, or matching placebo.

6.3.1. Initial 12 Week Treatment Period

Study drug and placebo will be taken as follows by study subjects:

5 mg CCX140-B (QD):

- One 5 mg CCX140-B and two matching placebo tablets in the morning dose, and three matching placebo tablets in the evening dose; doses should be approximately 10-12 hours apart and taken daily for 12 weeks (84 days).

10 mg CCX140-B (BID):

- Two 5 mg CCX140-B and one matching placebo tablets in the morning dose, and two 5 mg CCX140-B and one matching placebo tablets in the evening dose, doses should be approximately 10-12 hours apart and taken daily for 12 weeks (84 days).

15 mg CCX140-B (BID):

- Three 5 mg CCX140-B tablets in the morning dose, and three 5 mg CCX140-B tablets in the evening dose, doses should be approximately 10-12 hours apart and taken daily for 12 weeks (84 days).

Placebo:

- Three matching placebo tablets in the morning and three matching placebo tablets in the evening, approximately 10-12 hours after the morning dose, daily for 12 weeks (84 days). (The placebo tablets will be identical in appearance to the CCX140-B tablets).

6.3.2. Open-Label Treatment 12 Week Treatment Period

(Only applicable to subjects who are eligible and willing to participate in the Open-Label Extension, after Week 12).

Study drug will be taken as follows by study subjects:

Open Label Dose:

The dose for the open label phase of this study is planned to be 15 mg twice daily. If, during the course of the study, the Sponsor, together with the independent Data Monitoring Committee determines that 15 mg twice daily is exceeds the maximally tolerated dose, the open label dose will be adjusted downward.

6.4. Rationale for Dose Selection

The three active treatment doses proposed for the study are 5 mg administered daily, 10 mg administered twice daily, and 15 mg administered twice daily.

Five (5) mg daily is selected as the lowest dose that was tested and found to be both safe and to be associated with a clinically-meaningful therapeutic effect in subjects with diabetic nephropathy (DN) in Study CL005_140. A total of 332 subjects were enrolled in a randomized, double-blind, placebo-controlled clinical trial to evaluate the efficacy, safety and tolerability of 5 mg CCX140-B 5 and 10 mg CCX140-B compared to placebo, when administered for up to 52 weeks in subjects with DN. The Phase 2 trial met its primary endpoint by demonstrating that treatment with 5 mg of CCX140-B given orally once daily added to a standard of care (SOC) regimen of RAAS blockade treatment resulted in a statistically significant ($p=0.01$) improvement in UPCR, beyond that achieved with SOC alone. The maximum treatment effect (24% reduction) was reached at 12 weeks, and sustained reduction in albuminuria relative to placebo was observed over the full year (UACR at each one of the ten time points over the 52-week treatment period in the subjects who received 5 mg CCX140-B continuously for 52 weeks, were below

those of the SOC alone group). Both active treatment regimens were well-tolerated; no dose-related safety signals were reported.

Ten (10) mg twice daily is selected as an intermediate dose for exploration of dose response and to guard against losing the efficacious dose if 15 mg twice daily is associated with unexpected or intolerable toxicity. Using the rat as the more sensitive species based on exposure, the NOAEL in the 26-week rat study was 15 mg/kg/day. The NOAEL in the 13-week and 26-week rat studies were associated with systemic exposures to CCX140 which were about 9-10 times higher than the human exposure associated with a daily 10 mg dose, and about 4-5 fold a 10 mg BID dose.

Fifteen (15) mg twice daily is selected as the highest dose for this protocol, which is projected to provide exposure at both peak and trough that is within the safety margins established in the toxicology program, and that is projected to maintain a high level of target engagement, as summarized below and detailed in the Investigator's Brochure. The projected clinical exposure with 15 mg twice daily dosing is 3-fold below the NOAEL exposure established in the most sensitive species tested in the nonclinical toxicity studies (rat 26-week, PO, QD). In humans, CCX140-B has been administered and was well tolerated at 15 mg administered once daily for up to 10 days in healthy volunteers, and at 10 mg administered once daily for up to 52 weeks in subjects with DN. Administration of 15 mg twice daily in humans without proteinuria is projected to achieve a peak concentration of ~6500 ng/mL (~13 μ M) and a trough concentration of ~5500 ng/mL (~11 μ M) at steady state. Total exposure with 15 mg twice daily is projected to be ~2-fold higher than that achieved with 15 mg daily administration in healthy volunteers and 3.07-fold higher than that observed with 10 mg daily exposure in subjects with DN. Trough exposure with 15 mg twice daily is projected to be 2.4-fold higher than trough exposure achieved in DN.

Rationale for selection of 15 mg twice daily is to ensure adequate exposure margin to address:

1. Loss of albumin-bound drug through proteinuria; a post-hoc analysis PK in subjects of trial #CL005_140 who entered in study with albuminuria >1 gram indicated exposure was approximately 30% below the mean for the treatment group as a whole
2. Increased binding competition from endogenous ligand; MCP-1 is reported to be increased in serum and urine in subjects with FSGS

Rationale for administration of the highest dose as a divided dose (15 mg twice daily), as opposed to a single dose (30 mg once daily) include:

1. Ease of administration (3 tablets twice daily vs 6 tablets once daily)
2. 15 mg administered as a single daily dose has previously been tested and tolerated in healthy volunteers, while 30 mg has not been previously dosed
3. 15 mg twice daily will result in a lower C_{max} than 30 mg once daily, mitigating the potential for C_{max} -driven safety concerns

To ensure early detection of dose-related safety signals, the proposed protocol will incorporate:

1. Frequent clinical visits and safety laboratory assessments, including special attention to assessment of early indication of hemolysis (e.g. increased reticulocytes, increase from baseline in bilirubin or LDH) and application of a standard health assessment and a

questionnaire to detect symptoms of neuropathy at regular intervals as detailed in the [Time and Events Table](#).

2. Safety monitoring by an independent Data Monitoring Committee throughout the study.

6.5. Drug Supply

6.5.1. Packaging and Labeling

The investigational medicinal products (IMP) are oral film coated tablets containing 5 mg of CCX140-B and matching placebos. The tablets are manufactured under current good manufacturing practice. The clinical trial material is packaged in high density polyethylene (HDPE) bottles containing 30 tablets of either placebo or active. These bottles will be packaged in kits to administer to the subjects, in a blinded fashion; placebo, 5 mg once daily, 10 mg twice daily and 15 mg twice daily.

6.5.2. Storage

CCX140-B tablets will be stored according to label instructions. Access should be restricted to pharmacy staff or to the designated responsible member of the Investigator's staff, and to the study monitor. The Investigator agrees that neither s/he nor any of the study staff will supply study medication to any persons other than those enrolled in the study.

6.5.3. Blinding

This study is double-blind. Blinding of the study will be achieved by the following measures: The study drug bottles and tablet appearance for CCX140-B and its matching placebo will be identical.

Limited access to the randomization code; Sponsor personnel directly involved in the conduct and monitoring of the study, study site personnel, study subjects, personnel responsible for study monitoring, and biostatisticians and data managers involved in data analysis of the study will remain blinded to treatment assignment for the duration of the study.

While laboratory personnel conducting the PK assays will not be blinded to treatment assignment, unblinded CCX140-B plasma concentration results will not be shared with the study site personnel or study staff who have direct contact with study sites during the study.

Efficacy data that could potentially be unblinding, (i.e. UPCR, serum albumin and CBC) data within the normal range will not be made available to study site personnel, study subjects, personnel responsible for study monitoring, and biostatisticians and data managers during the study unless for safety monitoring. Investigators, however, will be provided with safety laboratory data reports, flagging abnormally high and low values to make informed decisions regarding subject care.

Treatment assignments for individual subjects will remain blinded to the study team, investigators, and subjects until after the study database has been cleaned and locked. Designated study staff will be provided with instructions regarding how to unblind an individual subject treatment assignment. An individual subject treatment assignment may be unblinded only in the case of an adverse event that requires knowledge of the study medication received by the subject

in order to provide appropriate treatment or management of the adverse event. The study monitor and Sponsor should be notified as soon as possible in the event that unblinding of an individual subject's treatment assignment occurs prior to study completion.

An external data monitoring committee (DMC) will be constituted prior to start of the study. The DMC members will review data periodically over the course of the study in an unblinded manner. The DMC will provide recommendations to the Sponsor regarding further conduct of the study. The DMC will operate according to a charter developed prior to study initiation.

6.6. Drug Accountability

The study pharmacist and Investigator must maintain accurate records of dates and quantities of product(s) received, to whom dispensed (subject-by-subject accounting), and accounts of any product accidentally or deliberately destroyed. The Investigator must retain all unused and/or expired study supplies until the study monitor has confirmed the accountability (bottle, study medication and diary reconciliation) data.

6.7. Treatment Compliance

The CCX140-B and matching placebo tablets will be self-administered by participating study subjects. The morning dose of study drug on Day 1 will be taken in the presence of study site personnel. Subjects will be provided with dosing instructions at the start of the study, and will be encouraged by study site personnel to take the study medication according to the instructions for the duration of the study. Subjects will be instructed to bring the assigned bottles of study medication to the site staff at each study visit, whether empty or not along with completed diaries. The study drug dispensed will be checked, and a tablet count will be done from Week 4 through the end of active study treatment of any remaining CCX140-B or placebo tablets. This information will be recorded and entered into the electronic data capture (EDC) system. Subjects who take less than 85% of their prescribed dose of study medication may be withdrawn from study due to treatment non-compliance.

CCX140-B plasma concentration measurements over the course of the study may also be used to assess subject compliance. Any events of non-compliance to the protocol will be documented in the study records and could result in withdrawal of the relevant subject.

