- The AIDS Clinical Trials Group Brief Peripheral Neuropathy Screening Tool Brief Peripheral Neuropathy Screening Tool (ACTG-BPNST) to assess early evidence of neuropathy;
- Monitoring for adverse events of infection;
- Alkaline phosphatase, ALT, AST and bilirubin (**total and direct**); to assess for evidence of drug induced liver injury.

For assessment of pharmacokinetics, study procedures will include

- Seven blood samples collected over 6 hours on Study Day 1 and at steady state (Study Day 15, or within 2 weeks thereafter) to assess AUC_{0-6} following the first administration of study drug, and at steady state;
- Assessment of C_{min} at intervals to ensure that exposure is within the projected range, with adequate safety margin based on the NOAEL established in preclinical toxicology;
- Upon discontinuation of treatment for any reason, collection of blood at 2 days, 7 days and 14 days following discontinuation to assess elimination.

All study procedures are presented in the [Time and Events table](#).

Subjects who are using an angiotensin converting enzyme (ACE) inhibitor, angiotensin receptor blocker (ARB) or other blocker of the renin angiotensin aldosterone system (RAAS), or who are using glucocorticoids, a calcineurin inhibitor or other immunomodulatory or immunosuppressive

[figure not shown]
therapy, should be on a stable dose for at least 4 weeks prior to screening. The dose of these medications must be kept constant over the course of the study in order to prevent undue influence of changes in these medications on the efficacy and safety assessments except when adjustment is required for patient well-being. The investigator must also attempt to keep doses of other medications, and lipid-lowering medications fixed throughout the blinded study period in order to prevent undue influence of changes in these medications on the efficacy and safety assessments.

Subjects who experience deteriorating renal function based on an increase in serum creatinine of at least 50% (confirmed by a repeat measurement after 2 weeks) which is otherwise not explained (e.g., dehydration, new medication), or increase in UPCR of >3.0 g/g (confirmed by a repeat measurement after 2 weeks) during the 12-week treatment period, will exit the treatment phase of the study and be treated at the discretion of the treating physician. All subjects who discontinue treatment will remain in the study for follow up and outcome recording.

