5.5. Removal of Subjects from Therapy of Assessment

Investigators must clearly distinguish between study drug treatment discontinuation and study withdrawal. Subjects who discontinue study drug treatment or who initiate medication changes (including those prohibited by the protocol) will not be automatically withdrawn from the study, but all efforts must be made to continue to follow the subjects for all regularly scheduled visits. The Medical Monitor should be contacted to determine how to address the specific situation.

Investigators must take appropriate measures to make sure that subjects are motivated to comply with all requirements of the protocol in order to minimize the amount of missing data. Subjects who discontinue study treatment early or initiate medication changes (including those prohibited by the protocol) should continue to be followed for all regularly scheduled visits for safety and efficacy assessments. Investigators and their staff must take measures to actively maintain contact with their subjects in the study, such as telephone calls, texts, or emails between visits, and offers for transportation support to visit the study site.

5.5.1. Subjects may be withdrawn from the study for the following reasons:

1. Subject withdrawal of consent to contribute additional outcome information;
2. Subject non-compliance with dosing or diary completion;
3. Loss to follow-up;
4. Sponsor's decision to terminate the study.

5.5.2. Subjects may discontinue study drug treatment for any of the following reasons:

1. Subject withdrawal of consent;
2. The Investigator may discontinue study drug treatment if, in his/her clinical judgment, it is in the best interest of the subject;
3. The Sponsor may request discontinuation of study drug treatment for safety reasons or non-compliance with treatment;
4. The Sponsor may request discontinuation of study drug treatment due to new or increased glucocorticoid/immunosuppressant treatment.

In the event of early withdrawal from the study, the tests and evaluations listed for the Early Termination visit in [Section 7.14](#) will be performed, whenever possible. Data collected at this visit will be designated as an "Early Termination" visit in the EDC. The Sponsor should be notified of all study drug treatment and study withdrawals in a timely manner.

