If the Investigator considers a change in background treatment for FSGS, this should be discussed with the Medical Monitor, and decision made regarding discontinuation of blinded

study drug. Independent of continuation or discontinuation of study drug, subjects should continue in the study for assessment of outcome.

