- **The subject will be given instructions and supplies for the urine collections on the day before the next visit (kit for first morning void and jug for 24-hour urine collection)**
 - **Collect the first morning void the day before the first visit (Day 0) and put in the smaller container.**
 - **Collect all urine for 24 hours starting AFTER the first morning void, including first morning void on the day of the Study Day 1 visit, in the big jug.**
 - **Keep specimens refrigerated until they are brought to the site at the Study Day 1 visit.**

7.2. Study Day 1

If eligible for the study, the subject will visit the study center on Day 1. The following procedures will be performed before taking the first dose of CCX140-B:

- A complete physical examination
- Vital signs (weight, temperature, blood pressure, heart rate after at least 3 minutes of rest)

- A 12-lead ECG, after at least 3 minutes of rest, will be recorded and assessed for any clinically significant abnormality
- Blood samples will be collected for serum chemistry (including coagulation panel and lipids), pregnancy test (in women of childbearing potential), hematology, DNA, plasma MCP-1, PK, PD (including lymphocyte subsets) and baseline measurements
- **Process the first morning void urine sample collection for quantitative urinalysis, UPCR, UACR, Cystatin C, Urine MCP-1, MCP-1/creatinine ratio and urine PD assessment**
- **Process the 24-hour urine sample collection for quantitative urinalysis, UPCR, UACR, Cystatin C, Urine MCP-1, MCP-1/creatinine ratio urine PD assessment and urine protein excretion/day**
- Any pre-treatment adverse events (from time of the screening visit) will be recorded
- Subjects will be asked to complete the SF-36 v2 and EQ-5D-5L
- Subjects will be asked to complete their diary each day immediately after each dose
- The ACTG Brief Peripheral Neuropathy Screening Tool will be administered

Once deemed eligible, the following procedures will be performed:

- Study medication (in kits, containing 4-week supply bottles of CCX140-B/Placebo), will be provided to the subject with dosing instructions
- The subject will be asked to take the first dose of CCX140-B while at the study center and should remain at the study center for observation at the PI's discretion
- The time of the dosing of CCX140-B will be recorded

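### Protocol sections 5.5.1 and 6.7 permit withdrawal from the study for dosing or diary non-compliance, which is inconsistent with the protocol's own follow-up rules and can lose Week 12 data unnecessarily

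*Protocol*

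**What the plan says.** **Passages that permit withdrawal from the study**

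- Protocol section 6.7: "Subjects who take less than 85% of their prescribed dose of study medication may be withdrawn from study due to treatment non-compliance".
- Section 6.7, next paragraph: "Any events of non-compliance to the protocol will be documented in the study records and could result in withdrawal of the relevant subject".
- Section 5.5.1, item 2 in the list of reasons for withdrawal from the study: "Subject non-compliance with dosing or diary completion". The diary standard is strict. Section 7.2 states: "Subjects will be asked to complete their diary each day immediately after each dose".

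**Passages that point the other way**

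- Section 5.5 tells investigators to keep treatment discontinuation and study withdrawal distinct, and gives limiting missing data as an aim. For subjects who stop drug or change medication, "all efforts must be made to continue to follow the subjects for all regularly scheduled visits". It repeats that those who stop treatment early or change medication "should continue to be followed for all regularly scheduled visits for safety and efficacy assessments".
- Section 5.5.2 item 3 lists non-compliance with treatment as a ground for the sponsor to ask that study drug be stopped, with no mention of leaving the study.
- Section 5.5.2, closing paragraph, on changes in background FSGS treatment: "Independent of continuation or discontinuation of study drug, subjects should continue in the study for assessment of outcome".
- Section 4, after the renal-deterioration exit rule: "All subjects who discontinue treatment will remain in the study for follow up and outcome recording".
- Section 6.8 keeps even a subject who needs rituximab or plasmapheresis in the study for outcome monitoring, off study drug.

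The SAP does not settle the matter. Section 3.4.1 runs the primary MMRM without imputation and relies on missing at random (MAR). Section 3.2.3 deals with compliance through the per-protocol set at 80% or more.

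**The concern.** Non-compliance with study drug has two different consequences in the protocol. Under 5.5.2 it can stop the drug; under 5.5.1 and 6.7 it can end observation. Two sites could treat identical subjects differently, and the subject who is withdrawn may have no Week 12 UPCR.

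With 10 subjects per arm each Week 12 value matters, and the sample-size section (protocol 9.4) states no dropout allowance. Tablet counts begin at Week 4 (6.7), while replacement is limited to subjects who discontinue in the first 14 days (5.1). A withdrawal based on those counts would therefore not be replaced.

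Low dosing can also be a consequence of how the subject is doing. The protocol's own halts for laboratory or clinical findings, and its stops for a confirmed creatinine or UPCR rise, reduce the number of tablets taken. The route to study withdrawal is therefore not obviously independent of toxicity or of the primary endpoint.

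**Working it through.** **1. The plan's own figure.** Inputs from protocol 9.4: SD 0.70 for change in log UPCR, 10 per group, two-sided alpha 0.10.

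Half-width = t(0.95, n1+n2−2) × SD × √(1/n1 + 1/n2)

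= 1.734 × 0.70 × √(1/10 + 1/10) = 0.543.

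At a ratio of 0.5 the interval is 0.5 × exp(±0.543) = 0.29 to 0.86. Both match protocol 9.4.

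**2. Who could fall below 85%.** Blinded treatment lasts 84 days, and 0.85 × 84 = 71.4 days. Section 6.7 does not define the prescribed dose. The SAP (3.3.7) divides tablets taken by 6 × the number of days in the period. If that period is the full 84 days:

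- One two-week halt under Table 2 (LDH, hemoglobin, reticulocytes, neuropathy or other significant events) leaves (84 − 14)/84 = 70/84 = 83.3%.
- A subject whose last dose is on or before Day 71 has at most 71/84 = 84.5%. This includes anyone stopped by then for a confirmed creatinine or UPCR rise, whom section 4 keeps in the study.

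If halted or post-discontinuation days are removed from the denominator, neither subject is below 85%. The text allows either count.

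**3. Effect on precision.** The documents give no withdrawal rate, so losses of 1 or 2 of 10 are assumptions. The same formula, with withdrawn subjects contributing nothing, gives:

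| n per group | t quantile | Half-width | Increase |
|---|---|---|---|
| 10 and 10 | 1.734 | 0.543 | – |
| 9 and 10 | 1.740 | 0.560 | 3% |
| 8 and 10 | 1.746 | 0.580 | 7% |
| 9 and 9 | 1.746 | 0.576 | 6% |
| 8 and 8 | 1.761 | 0.616 | 14% |

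In the worst of these cases (8 and 8), an observed ratio of 0.5 has a 90% interval of 0.27 to 0.93. For the losses assumed these are upper bounds, because the MMRM keeps the visits made before withdrawal.

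**4. Effect on bias.** MAR allows missingness to depend on treatment and on UPCR values already observed. The primary MMRM would be biased only if withdrawal depended on the unseen values after conditioning on the observed data. The three UPCR sensitivity analyses in SAP 3.4.1 vary the baseline definition, the urine source, and the handling of data after non-allowed medication. None varies the MAR assumption for subjects who leave the study. Protocol 9.3.5 mentions ANCOVA with LOCF as a sensitivity analysis, but the SAP, which supersedes it, carries that forward only for eGFR and only as an option.

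**The case against.** The strongest reply is that there is no flat contradiction. Withdrawal is discretionary. The follow-up sentences in 5.5 and section 4 literally concern subjects who discontinue drug or change medication, and the closing sentence of 5.5.2 follows a remark about background treatment. A subject still taking 82% of tablets has done none of these. Section 5.5 itself says only that such subjects are not withdrawn automatically, and it refers cases to the Medical Monitor. This stands. A reader might infer that the plan requires removal, or that it breaks a rule to follow every subject; the text supports neither. What remains is the inconsistency with 5.5.2 item 3, which gives treatment non-compliance a milder consequence, and with the stated aim of limiting missing data. For subjects whose low count comes from stopping drug, there is also a direct clash with section 4.

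Three further points on that side are fair:

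- A reader might infer that a late diary entry is enough for withdrawal. The text refers to completion of the diary; lateness follows only by combining it with the instruction in 7.2.
- A reader might see a conflict between 85% here and 80% for the per-protocol set. Over 504 tablets, someone taking 404 to 428 would meet the per-protocol compliance cut-off (0.80 × 504 = 403.2) yet fall below 85% (428.4). The two cut-offs serve different purposes, and leaving the study does not in itself remove a subject from the per-protocol set. This is not an error.
- Data are not wholly lost. Subjects withdrawn on tablet counts should already have UPCR at Weeks 1, 2 and 4. An Early Termination visit with UPCR is planned where possible, and SAP 3.1.2 can map it to Week 12 if it falls on Days 72 to 88. This reduces the loss but does not replace a Week 12 value for someone last seen before Day 72.

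**Conclusion.** The point holds as an inconsistency that should be resolved, with an effect of unknown size. The plan permits avoidable loss of Week 12 data, and under one reading of the prescribed dose its own two-week halt can bring a subject within reach of that provision.

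The precision cost is at most 3% to 7% on the half-width if 1 or 2 of 10 are lost in one arm, and 6% to 14% if they are lost in both. These figures rest on assumed losses and on withdrawn subjects contributing nothing.

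A reader might go further and infer that the primary MMRM is biased or that MAR fails. The documents do not support that. A link between withdrawal and treatment or observed UPCR is compatible with MAR, and dependence on unseen values is possible but not demonstrated. The narrower statement is that the listed sensitivity analyses would not reveal such a departure if it occurred.

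**What to change.** Reconcile the passages so that non-compliance does not end follow-up:

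1. Remove item 2 from the study-withdrawal list in 5.5.1.
2. In 6.7, replace both withdrawal statements (the 85% sentence and the broader one on any protocol non-compliance) with continued follow-up at all scheduled assessments for subjects who have not withdrawn consent. Changing only the 85% sentence would leave the provision in force.
3. Keep these subjects' data in the primary efficacy analysis (the mITT set in protocol 9.1.1, the set in SAP 3.2.2), with the per-protocol analysis already planned as secondary.

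This concerns observation only; it proposes no change to when study drug is halted or stopped.

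The cost is a protocol amendment across approximately 40 planned sites, with IRB/EC approval where section 11.4 requires it, and a few extra visits by non-adherent subjects. No new analysis is needed. SAP 3.3.1 already tabulates reasons for withdrawal by treatment group, which will show how often the provision was used.
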